Sample size for the primary objective (N=320; 160 per group) assumed equal allocation of participants to each treatment, type 1 error of 0.05 (2-sided), power=0.80 to detect an odds ratio of 1.77

Category percentages assumed in the design and given in the protocol are shown below in Table 1 for the primary ordinal outcome.

In the discussion that follows, unless otherwise stated, the numbers shown for both treatment groups combined include the 16 participants from the IVIG pilot study. These results are referred to as “FLU IVIG Pooled Outcome Data”.

Table 1

Outcome at Day 7	Percent in Each Category	
	IVIG	Placebo
Death	1.0	1.8
ICU (for FLU 003, assumed those ventilated were in the ICU)	2.1	3.6
Non-ICU hospitalization, O ₂	9.9	15.6
Non-ICU hospitalization, no O ₂	10.3	14.1
Discharged, not back to normal activities	38.4	39.0
Discharged, back to normal activities	38.2	25.8

As previously mentioned, the pooled FLU IVIG outcome data at day 7 after 170 participants were enrolled are similar to pooled data used in the design (see Table 2 below).

Table 2

Outcome at Day 7	Percent in Each Category	
	FLU IVIG Pooled Outcome Data (N=170)	Average of Design Estimates for the IVIG and Placebo Groups
Death	1.8	1.4
ICU	7.1	2.9
Non-ICU hospitalization, O ₂	10.6	12.8
Non-ICU hospitalization, no O ₂	7.6	12.2
Discharged, not back to normal activities	35.9	38.7
Discharged, back to normal activities	37.0	32.0

Pooled FLU IVIG outcome data (category percentages) at day 7 for 220 participants with influenza A infection as of April 30, 2018 are also similar to the overall category percentages above (see Table 3).

Table 3

Outcome at Day 7	FLU IVIG Pooled Outcome Data for Participants with Influenza A Infection (N=220)
Death	1.4
ICU	4.6
Non-ICU hospitalization, O ₂	10.5
Non-ICU hospitalization, no O ₂	8.2
Discharged, not back to normal activities	35.5
Discharged, back to normal activities	40.0

We assume that 232 of the participants ultimately randomized to FLU IVIG will be infected with influenza A. Assuming the design assumptions stated in the protocol and given in Table 1, with 232 participants, power is 0.67 to detect an odds ratio of 1.77 at the 0.05 level of significance (2-sided). An odds ratio of 1.95 can be detected with power=0.80 with 232 participants. The IVIG and placebo category percentages for participants with influenza A infection corresponding to an odds ratio of 1.95 are given in Table 4.

Table 4

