Outcome at Day 7	Participants with Influenza A; Assumed Percentages in Each Category	
	IVIG (N=116)	Placebo (N=116)
Death	1.0	1.8
ICU (for FLU 003, assumed those ventilated were in the ICU)	1.9	3.6
Non-ICU hospitalization, O ₂	9.1	15.6
Non-ICU hospitalization, no O ₂	9.7	14.1
Discharged, not back to normal activities	37.8	39.0
Discharged, back to normal activities	40.5	25.8

D. Analysis Set

The analysis set for the primary efficacy and safety analyses and all other analyses will exclude 21 randomized participants:

- 4 participants who declined to receive an IVIG/placebo infusion; and
- 17 participants at a single site in Thailand for whom eligibility based on the NEW score could not be confirmed and data alteration of the vital signs used to compute the NEW score was suspected.

One other participant (at a different site) did not meet strict eligibility criteria. This participant had a locally determined positive influenza test 4 days prior to randomization instead of within 2 days as stated in the protocol. This participant will be retained in the

primary analysis because this was not considered to be major, there was no evidence that it was intentional, and it is in keeping with the intention to treat principle. Thus, analyses in the final report will be restricted to 308 randomized participants. These analyses will be referred to as modified intention to treat.

For the primary efficacy analysis, missing day 7 outcomes (4 participants have missing outcomes among those infused) will be imputed for participants who were infused.

Sensitivity analyses will be carried out to assess the impact of including participants from the pilot study, to assess the impact of imputation for the primary outcome, and to assess the impact of the exclusion of participants from the site in Thailand.

The four sensitivity analyses are:

- 1) An analysis that excludes participants enrolled in the IVIG pilot (16 participants).
- 2) An analysis that excludes participants for whom the day 7 outcome is missing (4 participants).
- 3) An analysis that includes the 17 participants who may not have met the NEW score eligibility criteria at the site in Thailand.
- 4) An analysis that excludes all participants at the site in Thailand (80 total) for which the eligibility of 17 participants could not be confirmed.

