- The NEW score encompasses several factors that have been included as outcomes in recent influenza trials (e.g., normalization of respiratory rate and oxygen saturation, or clinical stability/clinical resolution that also considers temperature, heart rate, and systolic blood pressure).^{5,6,7} Considering this and the large number of participants discharged in the first 3 days, a second ordinal outcome with 5 categories was defined based on day 3 outcomes that includes the NEW score and does not consider whether participants discharged have resumed normal activities. The latter change was made because the outcome is assessed at day 3, shortly after the acute illness, when resumption of normal activities is less likely. The categorization by the participant of resumption of normal activities was also the most subjective component of the primary ordinal endpoint.

Key Secondary Endpoints

These 3 key secondary outcomes and the supportive efficacy outcomes will be used to compare all randomized participants in the primary analysis set of participants (see D. for definition) and in those with influenza A infection who are in the primary analysis set.

- Five category ordinal outcome on day 3:
 - Death
 - ICU
 - Non-ICU hospitalization, NEW score ≥ 3
 - Non-ICU hospitalization, NEW score < 3
 - Discharged
- Primary 6-category ordinal outcome on day 3
- Favorable outcome at day 7 taking in to account enrollment from the ICU or general ward (also referred to as a sliding dichotomy⁸) defined as:
 - ICU at enrollment to general ward or discharge before day 7
 - General ward at enrollment to discharge before day 7

Power Considerations for the Key Secondary Endpoints:

- For the 5-category ordinal outcome at day 3, an odds ratio of 1.78 can be detected with power = 0.80 at the 0.05 level of significance (2-sided).
- For the 6-category primary ordinal outcome at day 3, power is 0.80 to detect an odds ratio of 1.78.
- For the favorable outcome at day 7, power is 0.80 to detect a 12.5% absolute difference in the percentage with a favorable outcome at day 7 (86% versus 73.5%). For both treatment groups combined, approximately 80% have a favorable outcome at day 7.

The percentage of participants in the 5- and 6-category ordinal outcomes described above and that are basis for power estimates are given in Table 5 for both treatment groups combined as of May 23, 2018.

Table 5

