Outcome at Day 3	FLU IVIG Pooled Outcome Data at Day 3 (N=324)	Outcome at Day 3	FLU IVIG Pooled Outcome Data at Day 3 (N=323)
Death	0.3	Death	0.3
ICU	6.5	ICU	6.5
Non-ICU hospitalization, NEW score ≥ 3	17.3	Non-ICU hospitalization, on O ₂	21.4
Non-ICU hospitalization, New score < 3	34.0	Non-ICU hospitalization, not on O ₂	30.0
Discharged	42.0	Discharged, not back to normal activities	34.7
Not applicable (NA)	NA	Discharged, back to normal activities	7.1

In summary, with both the 5-category and 6-category day 3 ordinal outcomes, the odds ratio which can be detected with power=0.80 is approximately 1.77 (assuming 324 participants and a 2-sided type 1 error of 0.05). This is very similar to the odds ratio specified in the design (1.77) for day 7. Even if the proportional odds assumption is violated, power is expected to be similar to 0.80 if the overall assumed odds ratio is maintained. However, considering the category percentages in Tables 2 for day 7 and in Table 5 for day 3, the significance of the final result is likely to be more heavily influenced by differences in the non-ICU hospitalization and discharge (overall or not back to normal) categories at day 3 and by the differences in the two discharge categories (not back to normal and back to normal) at day 7.⁹

Analysis Considerations for the Key Secondary Outcomes

The analysis of the day 3 ordinal outcomes will follow the same plan as for the primary ordinal outcome at day 7. Logistic regression will be used to summarize the difference between the IVIG and placebo group in the favorable outcome at day 7. This model will be stratified by geographic region and include indicators for the participant's clinical status at entry (ICU, general ward on supplemental oxygen, general ward not on supplemental oxygen), and an indicator for whether the participant was in the IVIG pilot trial (FLU 005) or the FLU-IVIG trial (FLU 006).

For participants in the IVIG Pilot, the NEW score was not collected. It will be estimated using the reported vital signs each day. Level of consciousness was not collected. It will be assumed to be zero, therefore NEW scores for these participants may be underestimated. For participants in FLU-IVIG (FLU 006), NEW scores were to be collected twice daily through day 3 while hospitalized. Thus, the NEW score on day 3

will use the average of 2 readings if available, otherwise the single reading collected will be used.

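### The SAP states influenza A power for 232 randomized participants and day 3 power for 324, but its main analyses use 308, so these figures should be restated for the analysis set

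*SAP*

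**What the plan says.** SAP section A gives 329 randomized participants (313 plus 16 from the pilot). Section C makes the day 7 ordinal outcome in influenza A the main secondary objective and sets its denominator: "We assume that 232 of the participants ultimately randomized to FLU IVIG will be infected with influenza A". On that basis "with 232 participants, power is 0.67 to detect an odds ratio of 1.77 at the 0.05 level of significance (2-sided"), and "An odds ratio of 1.95 can be detected with power=0.80 with 232 participants". Table 4 carries this as 116 per arm.

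Section D excludes 21 randomized participants from the primary analysis and all others: 4 who declined the infusion and 17 at one site in Thailand. As a result "analyses in the final report will be restricted to 308 randomized participants". Section E applies the primary methods to influenza A. Section G compares the key secondary and supportive outcomes in the primary analysis set "and in those with influenza A infection who are in the primary analysis set".

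Section G also gives power for the key secondary endpoints. The detectable odds ratio is 1.78 for the 5-category day 3 outcome. For the other day 3 outcome, "For the 6-category primary ordinal outcome at day 3, power is 0.80 to detect an odds ratio of 1.78". The favorable outcome at day 7 (86% versus 73.5%) has power 0.80. The closing summary puts both day 3 odds ratios at about 1.77, "assuming 324 participants and a 2-sided type 1 error of 0.05".

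**The concern.** The power statements and the analysis set come from the same SAP, dated after enrollment closed, yet they use different denominators. The influenza A count is tied to everyone randomized, although section D drops 21 of them. About 70% of randomized participants are assumed to have influenza A (232/329 = 70.5%), so some of the 21 probably did. The day 3 mismatch needs no such assumption: 324 exceeds 308, so at least 324 − 308 = 16 of the people counted are excluded by section D.

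What is at stake is how the results are read. The influenza A power is a new element of the SAP and does not come from the protocol. It tells the reader what effect the main secondary comparison could detect. A null influenza A result would be set against a detectable odds ratio of 1.95, which the analyzed participants may not support.

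**Working it through.** **Inputs.** Two-sided alpha 0.05, 1:1 allocation and the Table 1 percentages (SAP section C); Table 5 percentages and the favorable-outcome rates (section G); 329 randomized (section A); 21 excluded and 308 analyzed (section D).

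**Formula.** The SAP cites Whitehead's method for ordered categories:

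- power = Φ( ln(OR) × √(N·w/12) − 1.96 )
- w = 1 − Σ p̄ᵢ³, where p̄ᵢ is the mean of the two arms' percentages in category i
- detectable OR at power 0.80 = exp( (1.96 + 0.84) × √(12/(N·w)) )

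From Table 1, w = 0.905 at an odds ratio of 1.77. For larger odds ratios the IVIG percentages, and so w, were recalculated.

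**Reproducing the SAP.**

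- N = 320: power 0.801 at 1.77 (stated 0.80).
- N = 232: ln(1.77) = 0.571 and √(232 × 0.905/12) = 4.18, so the product is 2.39. Φ(2.39 − 1.96) = 0.666 (stated 0.67).
- N = 232: detectable odds ratio 1.955 (stated 1.95); power at 1.95 is 0.797 (stated 0.80).

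**Influenza A within the 308.** The number with influenza A among the 21 is not reported, so the range is shown. Pro rata, the count is 232 × 308/329 = 217. If all 21 had influenza A, it is 232 − 21 = 211.

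| Influenza A among the 21 | N analyzed | Power at 1.77 | Power at 1.95 | Detectable OR |
|---|---|---|---|---|
| none | 232 | 0.666 | 0.797 | 1.955 |
| pro rata | 217 | 0.637 | 0.770 | 2.00 |
| all 21 | 211 | 0.625 | 0.759 | 2.02 |

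Each influenza A participant among the 21 therefore costs about (0.666 − 0.625)/21 = 0.002 of power. Simulating a tie-corrected rank-sum test (20,000 runs per setting) gave 0.663, 0.637 and 0.616 at N = 232, 217 and 211.

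**Day 3 outcomes.** The pooled Table 5 percentages give w = 0.8815 (5-category) and 0.9208 (6-category). Detectable odds ratios at power 0.80:

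| Outcome | N = 324 | N = 308 | Stated |
|---|---|---|---|
| 5-category | 1.776 | 1.802 | 1.78 |
| 6-category | 1.754 | 1.779 | 1.78 |

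**Favorable outcome at day 7.** Two proportions, 0.86 and 0.735 (mean 0.7975), with pooled variance under the null. At 154 per arm (308/2), the null standard error is √(2 × 0.7975 × 0.2025/154) = 0.0458. The alternative standard error is √((0.86 × 0.14 + 0.735 × 0.265)/154) = 0.0452. Power = Φ((0.125 − 1.96 × 0.0458)/0.0452) = 0.782. At 324 the same steps give 0.802, which matches the stated 0.80.

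**Primary outcome, for reference.** At N = 308, power at 1.77 is 0.786 and the detectable odds ratio is 1.79.

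**The case against.** The best defense is that nothing is miscalculated. The influenza A figures reproduce at 232, and the SAP openly calls that count an assumption. This is right: the fault lies in the denominator, not the arithmetic.

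A second argument is that the larger set is also analyzed. Sensitivity analysis 3 restores the 17 participants from Thailand, giving 308 + 17 = 325. Only the 4 uninfused participants are then missing, so that set holds 228 to 232 with influenza A, and power is 0.658 to 0.666. The printed 0.67 suits that analysis. But the SAP offers the figure for the main secondary objective, whose main analysis uses the 308.

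A third is that the numbers are too approximate for a few points to matter. The formula ignores covariate adjustment, and the pooled influenza A percentages in Table 3 alone give 0.659 at N = 232. With 0.67 the SAP already concedes power below 0.80, and 0.64 leads to the same conclusion. This limits the importance of the point but does not make 232 or 324 the right count.

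A reader might also infer that 320 is a wrong randomized count. The documents do not support that. The protocol gives 320 as the planned size and the SAP restates it as design history. Power of 0.80 at 1.77 is correct for that plan.

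**Conclusion.** The point holds as a mismatch of denominators. The influenza A power is stated for a randomized count and the day 3 power for 324, while the main analyses use 308.

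For influenza A the shortfall runs from zero to about 4 percentage points of power at 1.77, and is about 3 points pro rata. The detectable odds ratio lies between 1.955 and 2.02. It is tempting to say outright that the stated power is too high. The documents support only that this is likely, because the influenza A count among the 21 is not reported. Seventeen of the 21 come from one site, so pro rata removal is an assumption.

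At 308 the 5-category detectable odds ratio and the favorable-outcome power are slightly less favorable than stated, and the 6-category value is already right. A reader might see a contradiction between 1.78 and about 1.77 in section G. The difference is small and partly rounding, since the 5-category value at 324 is 1.776, and it is not a separate error.

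These sizes rest on the design percentages for day 7, the pooled percentages for day 3, and an unadjusted proportional odds calculation.

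**What to change.** - In section C, obtain the blinded count of influenza A participants within the 308, and restate power at 1.77, the detectable odds ratio and Table 4 for it. If the count is about 217, the values are 0.64 and 2.00.
- In section G, replace the assumption of 324 with 308. Give detectable odds ratios of 1.80 (5-category) and 1.78 (6-category) and power of 0.78 for the favorable outcome, and align the closing summary with them.
- Keep 320, power 0.80 and odds ratio 1.77 as the original design figure. A note that 308 gives about 0.79 would be a useful option.

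The only cost is slightly less favorable stated figures. No test, estimate, type 1 error or sample size changes, and no additional participants are needed.

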To supplement the overall summary odds ratio, separate odds ratios will be estimated for each dichotomized definition of improvement that can be formulated from the components of the ordinal outcome. A test for the proportionality assumption will also be made.

Analyses identical to those described above (including the imputation) will be carried out for participants with influenza A virus infection. If the central determination of influenza resulted in negative or indeterminate results, the local determination will be used. For participants with a co-infection with A and B influenza subtypes, the participant will be classified as A.

The analyses described above will be carried out for the primary efficacy analysis and for the two planned sensitivity analyses.

These analyses will be supplemented with summaries which give the category percentages for the primary ordinal outcome by treatment group for days 1-7.

F. Subgroup Analysis

Analyses will be carried out for the following baseline-defined subgroups:

- Influenza strain (A, B) and subtype (pH1N1, H3N2, B)
- Age (<40, 40-59, ≥ 60 years)
- Gender (men, women)
- Race/ethnicity (White/Hispanic/other, Black, Asian)
- Enrollment ward/use of O₂ (ICU, general ward on O₂, general ward not on O₂)
- Geographic region (United States/South America/Mexico, Europe/Australia, Thailand)
- Northern/Southern hemisphere/Equatorial (United States, Mexico, and Europe vs Australia and South America vs Thailand)
- Duration of symptoms prior to randomization (≤ 3, 4, ≥ 5 days)
- New score (≤ 3, 4-5, ≥ 6)
- Influenza season (Oct2013-Sep2014, Oct2014-Sep2015, Oct2015-Sep2016, Oct2016-Sep2017, Oct2017-Jun2018)
- Co-morbidities (CVD, COPD/asthma, diabetes, none of these) (as hierarchy)
- Other conditions (sepsis, pneumonia, immune suppression) (each considered separately versus not having the condition)

- Influenza strain/viral load (A and viral load > 100,000/≤ 100,000, B and viral load > 1,000,000/≤ 1,000,000) (4 categories)
- Influenza vaccination (yes, no, unknown)
- Smoking status (current smoker, non-smoker)
- IVIG lot (1-5)
- HAI titer (highest titer measured)
- HAI titer corresponding to subtype of infection (highest titer measured)
- Risk score tertile for hospitalization or death at day 7

The following special situations will apply to the categorization of participants for subgroup analyses:

- If central laboratory results are negative or indeterminate for influenza strain/subtype, the local laboratory result will be used for classifying strain/subtype.
- Influenza vaccination was recorded differently on different versions of the baseline case report form. Participants will be considered as vaccinated if they report being vaccinated in the past 6 months or report being vaccinated in the season of their enrollment.
- IVIG lot will be imputed for participants assigned to placebo using the lot of the closest (in time) enrolled participant who received IVIG at that site.
- For the risk score for hospitalization or death at day 7, the following baseline covariates will be considered: age, gender, race/ethnicity, geographic region, duration of symptoms prior to enrollment, status at enrollment (ICU, general ward on O₂, general ward not on O₂), vaccination in current season, influenza strain, comorbidities (see above), other conditions (see above), and season of enrollment. The score for each participant will be determined using a logistic model that includes participants from both treatment groups.

The interaction between each subgroup and treatment will be assessed with expanded proportional odds models. Terms for each subgroup and a cross-product term with treatment will be added to the proportional odds model described above for the primary analysis. Interaction p-values for age, duration of symptoms, risk score for hospitalization or death at day 7, and NEW score will be based on the measured variable (1 df) not the categorical variable.

G. Secondary Endpoints

Some new secondary efficacy endpoints were defined, some in the protocol were dropped, and some are now defined as supportive. Reasons for this are:

- Approximately 40% of participants were discharged by day 3.
- The NEW score at day 3 was only determined for hospitalized participants. Thus, measuring change in NEW score at day 3 (as originally defined in the

protocol) is potentially biased due to missing data.

- The NEW score encompasses several factors that have been included as outcomes in recent influenza trials (e.g., normalization of respiratory rate and oxygen saturation, or clinical stability/clinical resolution that also considers temperature, heart rate, and systolic blood pressure).^{5,6,7} Considering this and the large number of participants discharged in the first 3 days, a second ordinal outcome with 5 categories was defined based on day 3 outcomes that includes the NEW score and does not consider whether participants discharged have resumed normal activities. The latter change was made because the outcome is assessed at day 3, shortly after the acute illness, when resumption of normal activities is less likely. The categorization by the participant of resumption of normal activities was also the most subjective component of the primary ordinal endpoint.

Key Secondary Endpoints

These 3 key secondary outcomes and the supportive efficacy outcomes will be used to compare all randomized participants in the primary analysis set of participants (see D. for definition) and in those with influenza A infection who are in the primary analysis set.

- Five category ordinal outcome on day 3:
 - Death
 - ICU
 - Non-ICU hospitalization, NEW score ≥ 3
 - Non-ICU hospitalization, NEW score < 3
 - Discharged
- Primary 6-category ordinal outcome on day 3
- Favorable outcome at day 7 taking in to account enrollment from the ICU or general ward (also referred to as a sliding dichotomy⁸) defined as:
 - ICU at enrollment to general ward or discharge before day 7
 - General ward at enrollment to discharge before day 7

Power Considerations for the Key Secondary Endpoints:

- For the 5-category ordinal outcome at day 3, an odds ratio of 1.78 can be detected with power = 0.80 at the 0.05 level of significance (2-sided).
- For the 6-category primary ordinal outcome at day 3, power is 0.80 to detect an odds ratio of 1.78.
- For the favorable outcome at day 7, power is 0.80 to detect a 12.5% absolute difference in the percentage with a favorable outcome at day 7 (86% versus 73.5%). For both treatment groups combined, approximately 80% have a favorable outcome at day 7.

The percentage of participants in the 5- and 6-category ordinal outcomes described above and that are basis for power estimates are given in Table 5 for both treatment groups combined as of May 23, 2018.

Table 5

Outcome at Day 3	FLU IVIG Pooled Outcome Data at Day 3 (N=324)	Outcome at Day 3	FLU IVIG Pooled Outcome Data at Day 3 (N=323)
Death	0.3	Death	0.3
ICU	6.5	ICU	6.5
Non-ICU hospitalization, NEW score ≥ 3	17.3	Non-ICU hospitalization, on O ₂	21.4
Non-ICU hospitalization, New score < 3	34.0	Non-ICU hospitalization, not on O ₂	30.0
Discharged	42.0	Discharged, not back to normal activities	34.7
Not applicable (NA)	NA	Discharged, back to normal activities	7.1

In summary, with both the 5-category and 6-category day 3 ordinal outcomes, the odds ratio which can be detected with power=0.80 is approximately 1.77 (assuming 324 participants and a 2-sided type 1 error of 0.05). This is very similar to the odds ratio specified in the design (1.77) for day 7. Even if the proportional odds assumption is violated, power is expected to be similar to 0.80 if the overall assumed odds ratio is maintained. However, considering the category percentages in Tables 2 for day 7 and in Table 5 for day 3, the significance of the final result is likely to be more heavily influenced by differences in the non-ICU hospitalization and discharge (overall or not back to normal) categories at day 3 and by the differences in the two discharge categories (not back to normal and back to normal) at day 7.⁹

Analysis Considerations for the Key Secondary Outcomes

The analysis of the day 3 ordinal outcomes will follow the same plan as for the primary ordinal outcome at day 7. Logistic regression will be used to summarize the difference between the IVIG and placebo group in the favorable outcome at day 7. This model will be stratified by geographic region and include indicators for the participant's clinical status at entry (ICU, general ward on supplemental oxygen, general ward not on supplemental oxygen), and an indicator for whether the participant was in the IVIG pilot trial (FLU 005) or the FLU-IVIG trial (FLU 006).

For participants in the IVIG Pilot, the NEW score was not collected. It will be estimated using the reported vital signs each day. Level of consciousness was not collected. It will be assumed to be zero, therefore NEW scores for these participants may be underestimated. For participants in FLU-IVIG (FLU 006), NEW scores were to be collected twice daily through day 3 while hospitalized. Thus, the NEW score on day 3

will use the average of 2 readings if available, otherwise the single reading collected will be used.

If a NEW score is not available on Day 3, the last available follow-up NEW score will be used.

For the favorable outcome on Day 7, for the 4 participants who are missing the primary outcome on Day 7, it is presumed that they did not die or were re-hospitalized following discharge, i.e., they will be considered as having a favorable outcome.

H. Supportive Efficacy Endpoints

The following efficacy outcomes are defined as supportive:

- Time to discharge
- Time to death
- Percentage alive and out of the hospital at day 28
- Change in nasopharyngeal viral load from baseline to day 3
- Change in HAI titers from baseline to day 1, 3 and 7
- Percentage dying or requiring re-hospitalization after discharge
- Percentage with a diagnosis on or after the day of randomization and before the day 28 visit developing acute respiratory distress syndrome, acute renal failure, sepsis, pneumonia, enteritis or bronchitis (considered individually and also any of the diagnoses)
- Ordinal outcome on day 14
- Percentage alive and out of the hospital at day 14
- Resumption of normal activities at day 14.
- Ordinal outcome on day 28

Analysis Considerations for Supportive Efficacy Outcomes

Kaplan-Meier curves will be used to summarize the time to discharge and time to death, overall and through 7 days. The median number of days from randomization to discharge will be estimated. Deaths during hospitalization will be censored after day 28 (or day 7) for analyses of time to discharge. A logrank test will be used to compare treatment groups.

For participants who experienced multiple hospitalizations during follow-up, the time to the last discharge before day 28 will be considered. As the visit window for the day 28 visit extends to day 35, events after day 28 but prior to the final visit will be included in these analyses.

The difference between the IVIG and placebo group for change in log-transformed nasopharyngeal viral load from baseline to day 3 will be summarized using stratified analysis of variance with baseline viral load as a covariate. Viral loads vary by subtype. Therefore, strata will be defined by influenza virus subtype (H1N1, H3N2, or B) as well as geographic region. In these analyses, levels below 75 copies, the lower limit of detection, will be imputed as 75 copies. For this analysis, deaths (currently one

participant) on or before day 3 will be excluded, as will participants with undetectable RNA.

The IVIG and placebo group will also be compared for the percentage with undetectable viral RNA at day 3 using logistic regression with baseline viral load as a covariate and geographic region and influenza subtype as stratifying factors. For this analysis, exclusions will be as per the previous paragraph; however, participants dying on or before day 3 (currently one participant) will be included in these analyses and considered as having detectable RNA.

Ordinal outcomes will be summarized using a proportional odds model as described for the primary ordinal outcome (see E.).

Binary outcomes will be summarized with logistic models that are stratified by geographic region and include indicators for the participant's clinical status at entry (ICU, general ward on supplemental oxygen, general ward not on supplemental oxygen), and an indicator for whether the participant was in the IVIG pilot trial (FLU 005) or the FLU-IVIG trial (FLU 006).

Reference viruses used for HAI titers changed over the course of the study corresponding to the circulating viruses. Longitudinal random effects models stratified by subtype (H1N1, H3N2, B) will be used to estimate differences in log-transformed HAI titers between the IVIG and placebo group at days 1, 3 and 7. Baseline HAI levels will be included in these models as a covariate. Each HAI titer assessed will be used to compare the two treatment groups. In addition, analyses specific to the virus of infection, will be carried out. For participants infected with H1N1, A/California/2009 and A/Michigan/2015 will be used; for those infected with H3N2, A/Hong Kong/2014, A/Switzerland/2013 and A/Texas/50/2012 will be used; and for those infected with influenza B virus, B/Phuket/2013, B/Brisbane/2008 and B/Massachusetts/2012 will be used.

I. Safety Endpoints

Targeted symptoms are collected at baseline day 3 and day 7. Unsolicited grade 3 or 4 adverse events are collected on days 1-3, 7, 14, and 28. SAEs are collected throughout the 28 day follow-up. The following will be summarized:

- Percentage of participants for whom infusion was interrupted.
- Percentage of participants with adverse events of grade 3 or 4 severity.
- Percentage of participants with a serious adverse event (SAE).
- Percentage with a composite outcome of death, SAE, infusion interruption, or any grade 3 or 4 adverse event.
- Percentage of participants with each targeted symptom on day 3 and on day 7
- Change in serum chemistries and complete blood count (CBC) between baseline and day 7.

Analysis Considerations for Safety Outcomes

Adverse events will be compared for the IVIG and placebo groups and summarized using chi-square statistics stratified by geographic region. Serum chemistry and CBC measurements will be summarized as changes from baseline to Day 7 using analysis of covariance stratified by clinical site (local laboratories were used).

J. Baseline Characteristics

Tabulations will be prepared by treatment group for a number of baseline variables:

- Influenza subtype
- Age
- Gender
- Race/ethnicity
- Enrollment ward/use of O₂
- Geographic region
- Northern/Southern hemisphere/Equatorial
- Duration of symptoms prior to randomization
- New score
- Influenza season
- Co-morbidities
- Complications
- Subtype/viral load as defined for subgroups
- Influenza vaccination
- Smoking status
- Use of antiviral medication at time of randomization and of those given antivirals the percentage given oseltamivir.

Summary statistics will include N, mean, SD, median, 25th, 75th percentiles, and percentages for categorical variables. Categorical variables will be defined as for the subgroup analysis.

K. Infusion Summary

The following statistics will be used to summarize the infusion in each treatment group:

- Number and percentage of participants receiving complete infusion, partial infusion, or not infused.
- Among participants infused, the day of infusion (same day as randomization, next day, > 1 day after randomization).
- Among participants infused, time between randomization and beginning of infusion (median minutes, 25th, 75th percentiles).
- Among participants infused, estimated dosage administered (median mL, 25th, 75th percentile).
- Among participants receiving full infusion, duration of infusion (median minutes, 25th, 75th percentiles).
- Number and percentage of participants with a grade 3/4 AE or SAE during the infusion.

- Listing of problems reported during the infusion.

L. Completeness of Follow-up

According to protocol, participants are to be seen for data collection at day 1, 3 and 7 after randomization. In addition, data collection (by telephone or in person) was required at day 2, day 14, and day 28. The completeness of follow-up will be summarized by treatment group with the following statistics for the participants infused:

- Number and percent of participants attending each required visit.
- Number and percent of participants with known primary ordinal outcome at day 7.
- Number and percent of participants with known ordinal outcome at day 28.
- Number and percent of participants with known vital status at day 7.
- Number and percent of participants with known vital status at day 28.
- Listing of participants who withdrew consent, including dates of randomization, infusion, and date of withdrawal.

M. Assessment of Blinding

On the final visit (day 28 for most participants), an assessment of the treatment blind was made. Participants were asked to guess their treatment assignment and a staff member responsible for evaluating the participant's symptoms was asked to guess the participant's treatment assignment (IVIG or placebo).

The percentage of correct guesses by treatment group will be determined separately for study participants and for staff members.

N. Exploratory Analyses

If the IVIG and placebo groups differ for the primary ordinal outcome at day 7, either overall or for the subgroup of participants with influenza A infection, the time course of the differences in the 6-category ordinal outcome will be evaluated using longitudinal regression models. In addition, the extent to which the treatment differences can be explained by HAI titers and other biomarkers determined on stored specimens will be investigated.

References

- ¹ Lynfield R, Davey R, Dwyer DE, et al. Outcomes of influenza A(H1N1)pdm09 virus infection: results from two international cohort studies. *PLoS One* 2014; 9: e101785.
- ² Dwyer DE, Lynfield R, Losso MH, et al. Comparison of the outcomes of individuals with medically attended influenza A and B virus infections enrolled in 2 international cohort studies over a 6-year period: 2009-2015. *Open Forum Infectious Diseases* 2017; DOI: 10.1093/ofid/ofx212.
- ³ INSIGHT FLU005 IVIG Pilot Study Group. INSIGHT FLU005: An anti-influenza virus hyperimmune intravenous immunoglobulin pilot study. *JID* 2016; 213: 574-578.
- ⁴ Whitehead J. Sample size calculations for ordered categorical data. *Stat Med* 1993; 12: 2257-2271.
- ⁵ Ison MG, Hui DS, Clezy K, et al. A clinical trial of intravenous peramivir compared with oral oseltamivir for the treatment of seasonal influenza in hospitalized adults. *Antiviral Therapy* 2013; 18: 651-661.
- ⁶ De Jong MD, Ison MG, Monto AS, et al. Evaluation of intravenous peramivir for treatment of influenza in hospitalized patients. *CID* 2014; 59: e172-185.
